4.2 Rationale

4.2.1 Rationale of the trimodality approach

As stated in section 4.1.1, despite the promising results of SBRT, overall survival was not different between the two modalities and the relapse rate is still substantial. In a study by Senthil et al, 676 patients underwent SBRT for early stage lung cancer with a 2-year recurrence rate of 22% (6). Furthermore, of the 124 recurrences, 82 (66%) were distant recurrences. Looking at the preclinical and clinical data on the synergistic systemic antitumor effect of combination radiotherapy and immunotherapy, there is a strong biological rationale

to study these two modalities together as induction therapy for patients with operable early stage NSCLC.

In this protocol we will explore the addition of immunotherapy to SBRT to augment the antitumor T cell response, already associated with radiotherapy. This exploratory study aims primarily to assess the safety of the trimodality treatment strategy and to identify and characterize the immunological mechanisms of action of combined SBRT and anti-PD-1 treatment. Because the SBRT technique allows to irradiate small tumor volumes with maximal sparing of healthy lung tissue, this is the ideal and safest setting to introduce the combination of pulmonary radiotherapy and immunotherapy in lung cancer. The results of this study can serve as a proof of principle for the immunological effect of thoracic radiotherapy in general and might serve as a vehicle for further development of the combination of radiotherapy and immunotherapy in early stage lung cancer and stage III disease, a setting where radiation pneumonitis is a well-known and feared complication.

Because surgical resection is still the current standard of care for these patients, the subjects will undergo a lobectomy with hilar and mediastinal lymph node dissection after SBRT and pembrolizumab treatment. This is a key feature of this study and an unique opportunity to perform histological examination of the entire lung tumor and lymph nodes after immunotherapy, allowing to examine immune response heterogeneity and to correlate this with the non-invasive imaging and blood results. In the surrounding normal lung tissue, radiation and immunotherapy induced toxicity can be evaluated.

The goal of this study is to evaluate the safety and mechanisms of action of the novel trimodality treatment approach.

4.2.2 Rationale for Dose Selection/Regimen/Modification

Pembrolizumab will be administered intravenously 200 mg Q3W in this trial. The rationale for further exploration of 2 mg/kg and comparable doses of pembrolizumab in solid tumors is based on: 1) similar efficacy and safety of pembrolizumab when dosed at either 2 mg/kg or 10 mg/kg Q3W in melanoma patients, 2) the flat exposure-response relationships of pembrolizumab for both efficacy and safety in the dose ranges of 2 mg/kg Q3W to 10 mg/kg Q3W, 3) the lack of effect of tumor burden or indication on distribution behavior of pembrolizumab (as assessed by the population PK model) and 4) the assumption that the dynamics of pembrolizumab target engagement will not vary meaningfully with tumor type.

The choice of the 200 mg Q3W as an appropriate dose for the switch to fixed dosing is based on simulations performed using the population PK model of pembrolizumab showing that the fixed dose of 200 mg every 3 weeks will provide exposures that 1) are optimally consistent with those obtained with the 2 mg/kg dose every 3 weeks, 2) will maintain individual patient exposures in the exposure range established in melanoma as associated with maximal efficacy response and 3) will maintain individual patients exposure in the exposure range established in melanoma that are well tolerated and safe.

A fixed dose regimen will simplify the dosing regimen to be more convenient for physicians and to reduce potential for dosing errors. A fixed dosing scheme will also reduce complexity in the logistical chain at treatment facilities and reduce wastage.

4.2.3 Translational research

Because the mode of action of combined SBRT and anti-PD-1 therapy is unknown, it is essential to perform translational research to identify the mechanisms of action and toxicity before effect size studies can be initiated with recurrence free and overall survival as outcome parameters.

Serial invasive and noninvasive measurements of immune biomarkers will be performed for the primary tumor, lymph nodes and peripheral blood. A study schedule is provided in section 2.2. In short, the translational research will include:

- Biological imaging of tumor PD-1 expression in patients randomized to combination radiotherapy and pembrolizumab treatment with ⁸⁹Zr-pembrolizumab immuno-PET prior to treatment initiation. Biological imaging of PD-1 expression allows non-invasive *in-vivo* monitoring of PD-1 binding. To visualize PD-1 engagement by pembrolizumab we use a novel technique called immuno-PET in which positron emission tomography (PET) is combined with a radiolabeled monoclonal antibody. Imaging with radiolabelled pembrolizumab (⁸⁹Zr-pembrolizumab) allows for non-invasive quantification of its direct target, the PD-1 receptor on tumor infiltrating lymphocytes. Because the technique is non-invasive and whole body, it allows to evaluate tumor heterogeneity (volumetric analysis of tumor PD-1 expression).
- Immunohistochemical examination of immune effector subsets in a tumor core biopsy specimen at baseline. The following markers will be evaluated for expression: PD-1, PD-L1, CD4, CD8 and FoxP3, combined with Ki67 double staining.
- Multicolor flowcytometric assessment of immune effector subset rates and activation state in peripheral blood and TDLNs by means of endoscopic ultrasound guided fine needle aspiration (EBUS-FNA) at baseline and after SBRT +/- pembrolizumab treatment. The following subsets/populations will be included in this analysis: (memory/effector) CD4+ and CD8+ T cells, Tregs, granulocytic and monocytic MDSCs, conventional and plasmacytoid DCs, and macrophages.
- Three-dimensional tumor and lymph node histological examination of immune effector subsets in the resection specimen after SBRT +/- pembrolizumab treatment. This enables to
 - Explore intratumor heterogeneity of immune effector subsets after SBRT +/- pembrolizumab treatment, possibly associated with therapeutic resistance.
 - Correlate the 3D ⁸⁹Zr-pembrolizumab PET image results with the 3D primary tumor histopathology results and the lymph node histopathology results.
- In the lobectomy specimen the tumor surrounding healthy tissue will be examined for radiation induced changes.

4.2.4 Rationale for Endpoints

This an exploratory study that aims to evaluate the safety of the trimodality approach and characterize the immunological mechanisms of action of combination radiotherapy and immunotherapy. Therefore the primary endpoints of this study are the tolerability and toxicity of combined SBRT +/- pembrolizumab treatment and surgery and to analyze the immunological antitumor response. The endpoints will be assessed by clinical signs of

radiation pneumonitis and examination of tumor core biopsies and resection material, FACS analysis on EBUS-FNA of TDLNs and peripheral blood to detect immunomodulation.

Secondary endpoints are the correlations of *in-vivo* PD-1 expression, quantified by immune-PET, with tissue and blood based immune-parameters.

The levels of PD-1 and PD-L1 expression are variable over time (see section 4.1.8) and expression has been found to be heterogeneous between and within tumor lesions of the same patient. The biomarker PD-L1 IHC is currently being validated in multiple clinical studies to stratify patients based on the intensity and percentage of positive staining. This trial is a unique opportunity to study the 3-dimensional uptake of ⁸⁹Zr-pembrolizumab in the tumor and correlate the imaging result with the 3D immunohistochemistry results of the surgical tumor specimen.

Although pneumonitis will be assessed as a symptom, an exploratory objective is to evaluate radiation induced changes to healthy lung tissue after SBRT +/- pembrolizumab treatment in the resected lung lobe.

The number of patients (n=10 in each arm) is too low to correlate study parameters to clinical outcome in terms of progression-free or overall survival.

4.2.5 ⁸⁹Zr-pembrolizumab imaging

To identify patients that will benefit the most from treatment with mAbs like pembrolizumab, better knowledge of the *in vivo* behavior of the drug is warranted. For this, positron emission tomography (PET) imaging with radiolabeled mAbs (immuno-PET) is an attractive option.

The ability of PET to quantitatively image the distribution of radiolabeled drugs within the body makes this technique a valuable tool for drug development and application. Immuno-PET allows to learn about the ideal drug dosing for optimal tumor targeting (e.g., saturation of receptors), the uptake in critical normal organs to anticipate toxicity, and the variation in pharmacokinetics and tumor targeting. Drug imaging is able to provide this information in an efficient and safe way. Pretreatment imaging with the drug of interest can be used for patient selection because it can show target expression and drug accumulation in tumor lesions and normal tissues noninvasively, quantitatively, and over time. This information might be particularly relevant for heterogeneous target expression or when targeted drugs are combined with other treatment modalities like parallel pathway inhibition, to find routes of synergism. In this way, immuno-PET can be used for better understanding of *in vivo* biology (“immunohistochemistry *in vivo*”) (50).

To enable visualization of a targeted drug with a PET camera, the drug should be labeled with a positron emitter in an inert way, i.e., that neither binding nor pharmacokinetic characteristics of the drug become altered. Moreover, the physical half-life of the positron emitter should be compatible with the residence time of the targeted drug in the body, which is typically several days for slow kinetic intact mAbs. Universal procedures exist for radiolabeling of intact mAbs with the long-lived positron emitter Zirconium-89 (⁸⁹Zr, t_{1/2} = 78.4 h) (51).

During the past years, several preclinical and clinical ⁸⁹Zr-immuno-PET studies have been performed with intact mAbs, for example with mAbs against cMET, EGFR, VEGF and HER2 (52-55).

The first clinical ⁸⁹Zr-immuno-PET study ever was reported in 2006 by Börjesson et al. (56). This feasibility study with 20 head and neck cancer patients showed that ⁸⁹Zr-cmAb, directed

against CD44v6, can be safely applied in patients and that it is a promising tool for PET detection of primary tumors as well as of metastases in the neck. There was good agreement between tumor uptake derived by PET and that derived by tumor biopsy. This suggests that patients with high and low mAb uptake can be differentiated, which might be important for the selection of patients with the highest chance of benefit from mAb therapy. High quality images were obtained in an immuno-PET study with ⁸⁹Zr-trastuzumab in breast cancer patients (57). Excellent visualization of mAb uptake in HER2-positive lesions as well as in metastatic liver, lung, bone, and even brain HER2-positive lesions was observed. ⁸⁹Zr-trastuzumab PET allowed the quantification of conjugate uptake in HER2-positive lesions, and it became clear that for some patients with extensive tumor load, no HER2 saturation occurred during trastuzumab therapy. There was a good correlation between ⁸⁹Zr-trastuzumab tumor uptake and response as assessed by CT, MRI, and bone scans.

Biological imaging of the PD-1 pathway with ⁸⁹Zr-pembrolizumab allows to visualize the PD-1/PD-L1 pathway and non-invasive quantification of its direct target, the PD-1 receptor on tumor infiltrating lymphocytes. Because the technique is non-invasive and whole body, it allows for serial measurements of tumor uptake as well as looking at heterogeneity within and between tumor lesions.

We hypothesize that ⁸⁹Zr-pembrolizumab tumor uptake is heterogeneous within the tumor of individual patients and between tumor lesions of different patients and that uptake is related to PD-1 expression, PD-L1 expression. When a good correlation is found, ⁸⁹Zr-pembrolizumab PET might be used in other clinical settings to validate PD-1 and PD-L1 IHC as predictive biomarker of treatment benefit and to elucidate why some patients with positive PD-L1 IHC do not achieve a favorable tumor response and some patients with negative PD-L1 IHC do.

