2.2 Trial Diagram

3.0 OBJECTIVES & HYPOTHESES

3.1 Primary Objectives & Hypotheses

Objective 1:

To assess the safety of combined SBRT and pembrolizumab treatment.

Objective 2:

To identify the immunological response to combined SBRT and pembrolizumab treatment in early stage NSCLC. Expression rates and activation states of immune effector subsets will be assessed in tumor core biopsy specimens, peripheral blood and tumor draining lymph nodes (TDLNs) by means of EBUS derived fine needle aspirates. Samples will be taken before and after SBRT +/- pembrolizumab treatment and at surgery.

Hypothesis 2:

We anticipate that SBRT and pembrolizumab treatment will alter the immune activation status as well as the cellular composition in TDLNs, tumor and blood reflected by local and/or systemic switches from a suppressive immune content to a more activated immune content. The magnitude of this response is higher in the combination SBRT and pembrolizumab group than in the SBRT monotherapy group.

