5.6.3 Surgical resection

Surgery will occur 8-10 weeks following SBRT +/- pembrolizumab treatment. Surgery will consist of a lobectomy and may employ either an open approach or a video-assisted thoracoscopic approach. Surgical sampling of ipsilateral hilar and mediastinal lymph nodes at the time of resection is mandatory.

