6.0 TRIAL FLOW CHART

6.1 Study Flow Chart

Trial period	Screening Phase	Imaging	Induction treatment phase	Surgery	Follow-up
Scheduling Window (Days)	-30 to -1	-14 to 0	From day 1 to day 56 (2 weeks after 2 nd pembrolizumab cycle)	From day 56 to day 70	From surgery to 6 months thereafter
Administrative Procedures					
Informed Consent	X				
Eligibility Criteria	X				
Demographics and Medical History	X				
Prior and Concomitant Medication Review	X				
PET Imaging					
⁸⁹ Zr-pembrolizumab		X ^a			
Clinical Procedures/Assessments					
Review Adverse Events	X		X ^b		
Full Physical Examination	X				
Directed Physical Examination	X		X ^b		X ^c
Vital Signs and Weight	X		X ^b		
ECOG Performance Status	X		X ^b		
12-lead ECG	X				
¹⁸ F-FDG PET-CT		X		X	
Laboratory Procedures/Assessments					
Pregnancy Test	X				
Complete Blood Count (CBC)	X	X ⁱ	X ^b		
Comprehensive Serum Chemistry Panel	X		X ^b		
Urinalysis	X				
T3, FT4 and TSH	X		X ^d		
Treatment					
SBRT			X		
Pembrolizumab			X ^a		
Surgery				X	
Efficacy Measurements					
Tumor Imaging (CT thorax +/- abdomen and MRI brain)		X	X ^e		X ^f
Tumor Tissue and Blood analysis					
Core tumor biopsy	X				
EBUS FACS		X	X ^g		
Surgical resection specimen				X	
Immunophenotyping		X ^h	X ^h	X ^h	X ^h

X^a: only for patients randomized to the SBRT + pembrolizumab arm; X^b: every cycle; every 6 weeks; X^c: if indicated; X^d: after 2nd pembrolizumab cycle; X^e: within 2 weeks of surgery; X^f: following resection every 3 months for the first 2 years and every 6 months for the 3 years thereafter; X^g:; X^g:between week 2 and 3 after SBRT; . X^h: see section 7.1.2.10 for timepoints; Xⁱ: 72 and 144 hours post-injection for patients undergoing ¹⁸F-FGD-PET-CT

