8.5 Correlation between PET data and Blood and Tissue markers

The correlation between the continuous variable SUV and the categorical variables tissue PD-1 and PD-L1 IHC will be assessed with the ANOVA test. The correlation between the continuous SUV and blood variables will be assessed with the paired t-test.

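### The 89Zr-pembrolizumab PET precedes treatment but the tissue named for comparison is resected after it; section 8.5 does not commit to the pre-treatment biopsy, and its ANOVA discards the order of the IHC score

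*Combined protocol and SAP*

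**What the plan says.** **Scan.** Section 4.2.3 places the "immuno-PET prior to treatment initiation" and limits it to patients randomised to the combination. The flow chart (6.1) marks it only in the imaging column, day -14 to 0, with a footnote restricting it to that arm. Section 5.3.2.5 describes two scans, at 72 and 144 hours after injection. No later 89Zr scan is scheduled; the PET-CT marked at surgery uses 18F-FDG.

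**Tissue.** Section 4.2.3 lists, among the things the resected specimen makes possible, correlating the 89Zr images "with the 3D primary tumor histopathology results and the lymph node histopathology results". Section 4.2.4 likewise intends to study uptake "in the tumor and correlate the imaging result with the 3D immunohistochemistry results of the surgical tumor specimen". Surgery is scheduled "From day 56 to day 70". Sections 7.1.2.7.1 and 8.2.1 also provide for IHC on a newly taken, mandatory pre-treatment biopsy, with the same markers as the resected tumour.

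**Expected change.** Hypothesis 2 in section 3.1 reads: "We anticipate that SBRT and pembrolizumab treatment will alter the immune activation status as well as the cellular composition in TDLNs, tumor and blood". Section 4.2.4 adds: "The levels of PD-1 and PD-L1 expression are variable over time".

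**Analysis.** Section 8.5: "The correlation between the continuous variable SUV and the categorical variables tissue PD-1 and PD-L1 IHC will be assessed with the ANOVA test". It names no tissue time point. Section 7.1.2.7.2 scores IHC on an ordered scale from 0 (absent) to 3 (extensive).

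**The concern.** Hypothesis 1 in section 3.2 expects uptake to be related to PD-1 and PD-L1 expression. Section 4.2.5 adds that a good correlation could support using the PET in other settings to validate IHC biomarkers. For that reading, uptake and tissue should describe the same tumour state. The tissue named for the comparison has been through the very treatment that is expected to change it. A weak correlation then has two explanations that this comparison cannot tell apart: the tracer does not track its target, or the target changed after the scan.

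The biopsy is the only tumour tissue from the same treatment state as the scan. Section 8.5 leaves open whether it is used, so the choice could be made after the results are known.

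A second, smaller matter is the test. Section 8.5 is titled as a correlation, but ANOVA treats the score as unordered and reports neither the direction nor the strength of the association. With about 10 patients the lost efficiency is noticeable.

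**Working it through.** The plan gives no power, effect size or alpha for this analysis, and section 5.2 says a formal power calculation was not feasible. There is no stated figure to reproduce.

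**1. Timing (flow chart, 6.1).** Scan window day -14 to 0; surgery day 56 to 70; biopsy in screening, day -30 to -1.
- Scan to resection: shortest 56 - 0 = 56 days; longest 70 + 14 = 84 days, with SBRT and up to two pembrolizumab cycles between.
- Biopsy to scan: at most 30 days (day -30 to day 0), with no trial treatment between.

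**2. What the resection comparison can show.** Let r be the correlation of uptake with the marker at the time of the scan, and s the correlation of the marker at scan with the marker at resection. If the resected marker depends on uptake only through its value at scan, the expected correlation is r × s. Then 0.8 × 0.6 = 0.48 looks the same as 0.48 × 1.0: resection data alone identify only the product. The documents give neither factor. For r = 0.8 and s = 1.0, 0.8, 0.6, 0.4, 0.2, the expected correlation is 0.80, 0.64, 0.48, 0.32, 0.16. Spearman power (10 patients, four equally frequent scores, two-sided 5%) is about 75%, 45%, 24%, 13%, 7%.

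The same algebra applies to the biopsy, with s as the fidelity of a core sample to the whole tumour. For r = 0.7 and a factor of 0.9, 0.8, 0.7 or 0.5 from either source, Spearman power is about 43%, 33%, 25% or 15%. The biopsy removes the treatment explanation, not the sampling one.

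**3. ANOVA against Spearman.** Simulation with 20,000 runs per setting, 10 patients, one value each, latent bivariate normal data, tissue cut into four ordered scores, two-sided 5%. With all four scores present, ANOVA has 3 and 6 degrees of freedom. Correlations and score shares are assumptions.

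| Score shares (0/1/2/3) | Latent correlation | Spearman | ANOVA | Difference (points) |
|---|---|---|---|---|
| 25/25/25/25% | 0.5 | 26.8% | 15.5% | 11.3 |
| | 0.7 | 54.4% | 33.8% | 20.6 |
| | 0.8 | 74.5% | 52.7% | 21.8 |
| 50/30/15/5% | 0.5 | 24.0% | 15.6% | 8.4 |
| | 0.7 | 48.1% | 33.6% | 14.5 |
| | 0.8 | 67.2% | 50.8% | 16.4 |
| 10/40/40/10% | 0.5 | 25.4% | 17.3% | 8.1 |
| | 0.7 | 52.6% | 38.8% | 13.8 |
| | 0.8 | 70.4% | 58.2% | 12.2 |

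At zero correlation both tests reject in about 5% of runs, so ANOVA is valid. If IHC is split into two equal groups (latent correlation 0.7), ANOVA has about 42% and Spearman about 44-45%. With a 14/86 split (100 - 86, from the 86% PD-L1 positive in advanced disease in section 4.1.8), ANOVA is ahead, about 23% against 16%.

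**4. Precision.** For an observed rho of 0.7 and n = 10, use Fisher's z with variance (1 + r²/2)/(n - 3) = 1.245/7 = 0.178, so the standard error is 0.422. Then z = 0.867 ± 1.96 × 0.422 = 0.867 ± 0.827, which gives a 95% CI of about 0.04 to 0.93.

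**The case against.** **The plan may already cover the biopsy.** Section 8.2.1, headed as tumour tissue, takes in both biopsy and resection, and section 4.2.4 speaks of tissue-based parameters shortly after listing both. A reader might infer that 8.5 excludes the biopsy; the text does not support that. What stands is that 8.5 makes no commitment, while 4.2.3 and 4.2.4 name only the resected tissue as the partner for the PET.

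**The resection comparison is deliberate.** Correlating imaging with the whole resected tumour is a stated purpose (sections 1.0, 2.1, 4.2.1). Hypothesis 1 concerns the whole tumour and its regions, which a core biopsy cannot represent. This stands in full: the biopsy belongs beside the resection comparison and cannot replace it.

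**The ANOVA loss depends on a four-level score.** Section 8.5 says only that the variables are categorical, and the 0-3 scale is written out under the resection specimen. This stands too: with two groups the loss nearly vanishes or reverses.

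**It is exploratory and small.** True, and there is no decision rule. But section 4.2.4 makes these correlations the secondary endpoints, and a small sample absorbs ambiguity badly.

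**Conclusion.** The point holds as a matter of interpretation and efficiency in a secondary, exploratory analysis. The timing argument rests only on the flow chart and on the protocol's own expectation that treatment alters the tumour. The ANOVA cost, roughly 10 to 20 points (8 to 22 across the settings tried), rests on an assumed four-level score, 10 patients and a latent correlation of 0.5 to 0.8.

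Four stronger readings are tempting but not supported:
- *Most resected specimens will hold no tumour to score.* Section 4.1.7 reports viable tumour in two of five, but these are unpublished patients from another trial, treated with SBRT and surgery without pembrolizumab; the exact 95% CI for 2/5 is 5% to 85%. The tracer's direct target is PD-1 on lymphocytes (4.2.3), which may stay scorable.
- *The gap is longer than 84 days.* Section 5.6.3 says "Surgery will occur 8-10 weeks following SBRT +/- pembrolizumab treatment", which could be counted from the second cycle. Counted from the start of treatment it matches the flow chart (8 × 7 = 56, 10 × 7 = 70). The wording is ambiguous, but 56 days already makes the point.
- *At most 10 patients have a scan.* Section 5.11 replaces those who do not complete the trimodality treatment, so more may be scanned and biopsied.
- *The biopsy would give more power.* Nothing in the documents shows this.

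**What to change.** In section 8.5:

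1. Add the baseline-biopsy PD-1 and PD-L1 scores as the time-matched comparison with tumour 89Zr SUV, one value per patient.
2. When IHC is on the 0-3 scale, replace ANOVA by Spearman's rho, or another ordered-trend method, with a 95% CI.
3. Keep the resection comparison, whole-tumour and regional, and label it *pre-treatment uptake against post-treatment tissue*. State that a null result there alone will not be read as failure of the PET to reflect PD-1/PD-L1. If several segments per patient are analysed, account for clustering by patient.

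The cost is SAP wording only: biopsy IHC, resection IHC and tumour SUV are already planned, with no new procedure, visit or patient. The downsides are real. A core biopsy samples only part of a heterogeneous tumour, so its correlation is attenuated as well. If both comparisons are weak, the result remains ambiguous. The timing gap cannot be repaired for the regional question, and with about 10 patients the intervals remain wide.
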